10.2. Eligibility Screening for WP1

Participating research sites will be required to complete a non-registration log of all patients who have been referred from general practice for CXR who fulfil the NG12 criteria and are considered potentially eligible for the study on the basis of their X-ray request but not recruited into the study. Documented reasons for ineligibility or declining participation will be collected and closely monitored by the CTRU as part of the regular review of recruitment progress. Non-registration logs should be returned to CTRU on a monthly basis. The following anonymised data will be collected on the non-registration log:

- Age
- Sex
- Index of multiple deprivation (according to participant's postcode)

- Ethnicity
- Date screened

Patients who are not registered either because they are ineligible or because they decline participation will also have the following recorded:

- Reason not eligible OR
- Reason declining participation
- Main language
- Whether or not the patient agrees to take part in WP3 including contact details and preferred method to receive further information

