12.10. Site level imaging data

As the ability of the radiology services to meet demand for LDCT depends on a number of complex factors, in one or more sites we will collate some additional data which may include staffing levels, number of operational x-ray and CT machines, planned elective capacity, but also the non-attendance and cancellation rates, equipment unavailability due to breakdown and maintenance, cancelled lists for other reasons (e.g. staffing), as well competing priorities as any emergency or surveillance CT activity that takes place on elective CT lists. We will collate this for at least two non-consecutive months.

We will capture data from selected participating site(s) on site-level imaging capacity according to established methodology[32-36]:

- Total number of CT examinations (chest and other) undertaken per week
- Total number of CXR examinations (GP requested and total) undertaken per week
- Number of full-time equivalent radiographers and radiologists on rota per week.
- Proportion of CXR requests received that fulfil NG12 criteria on one day per week (week 1 = Monday, week 2 = Tuesday etc.)

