As a feasibility study, MEDLEY has not been designed for any pre-specified precision (which would be the design criteria for a definitive trial). With a prevalence estimated as 1.7%, an estimated sensitivity of 90% would have an 95% exact confidence interval covering values as low as 72% (estimated using the Clopper-Pearson exact method). Other metrics including specificity of CXR/LDCT, proportions of concordant/discordant imaging results, proportions completing imaging, and proportions completing questionnaires would all have 2-sided 95% confidence intervals +/- 3.3% (estimated using the normal approximation method) assuming that a minimum of 97% of participants are included in estimates of specificity, and assuming a worst-case estimate of 50% where estimated variance is maximised.

We have used simulation to predict how precisely we will estimate the proportion of CXR requests that fulfil NG12 criteria. Assuming that there will be at least 169 centre-weeks of recruitment and that for each of these, GP CXR requests will be assessed for NG12 and those eligible contacted until 5 potential recruits are identified, we expect to estimate the proportion of requests fulfilling NG12 with a 95% confidence interval width of 2.4%, with the interval width being below 3.0% with 90%

probability. The simulation incorporated uncertainty in the population proportion of CXR requests fulfilling NG12 criteria (Beta distribution with parameters 31 and 69) and the proportion of CXR requests which do fulfil NG12 criteria resulting in a potential recruit (Beta distribution with parameters 5 and 5).

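### The 2.4-point interval width for the NG12 proportion (15.2) rests on a count of chest X-ray requests that the data-collection sections do not record

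*Protocol*

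**What the plan says.** Protocol 15.2 (Sample Size) gives a simulated precision for the share of GP chest X-ray requests that meet NG12: "we expect to estimate the proportion of requests fulfilling NG12 with a 95% confidence interval width of 2.4" per cent, "with the interval width being below 3.0% with 90" per cent probability. The sampling scheme behind it is set out in the same paragraph. It begins "Assuming that there will be at least 169 centre-weeks of recruitment", and within each centre-week "GP CXR requests will be assessed for NG12 and those eligible contacted until 5 potential recruits are identified". Two uncertainties are simulated: the "population proportion of CXR requests fulfilling NG12 criteria (Beta distribution with parameters 31 and 69"), and the chance that a request meeting NG12 yields a potential recruit, Beta(5, 5).

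Three other places bear on how this proportion would be recorded.

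- **10.2 (Eligibility Screening for WP1):** the non-registration log, returned monthly, covers patients "who fulfil the NG12 criteria and are considered potentially eligible for the study on the basis of their X-ray request but not recruited".
- **12.10 (Site level imaging data):** the listed item is "Proportion of CXR requests received that fulfil NG12 criteria on one day per week (week 1 = Monday, week 2 = Tuesday etc".), to be captured at selected participating site(s). The preceding paragraph, on staffing, machines and lost capacity at one or more sites, ends "We will collate this for at least two non-consecutive months".
- **14.1.3 (Imaging logistics):** repeats the one-day-per-week item as an outcome, with no number of sites or weeks.

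**The concern.** The precision in 15.2 describes one way of sampling requests, and the data-collection sections describe another. The simulated scheme runs in every recruiting centre-week and stops at the fifth potential recruit. The described scheme samples one weekday at an unspecified number of sites for an unspecified number of weeks. The one study-wide screening record omits requests that were assessed and did not meet NG12. At the assumed 31%, those are about 69% of the denominator.

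This is more than a detail for the statistical analysis plan, because no analysis can recover a denominator that was not collected. The proportion matters for planning: 15.3 estimates the extra CT tests needed if all NG12 requests were converted to LDCT. Section 6.5 applies 31% to 1,818,905 GP chest X-rays a year, so each percentage point is about 18,200 scans. A 2.4-point interval spans about 44,000 scans and a 9.1-point interval about 166,000.

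**Working it through.** **Inputs.** From 15.2: 169 centre-weeks, 5 potential recruits each, NG12 proportion Beta(31, 69) with mean 0.31, conversion to potential recruit Beta(5, 5) with mean 0.50, and 250–579 requests per site per week. From 12.10: one day per week.

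**1. Reproducing the stated figure.** At the mean values the number of requests assessed is

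N = (169 × 5) / (0.31 × 0.50) = 845 / 0.155 ≈ 5,452, about 32 per centre-week.

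The 95% interval width is 2 × 1.96 × √(p(1 − p)/N) = 3.92 × √(0.2139/5,452) ≈ 2.46 points.

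In a simulation of 200,000 studies, with both Beta variables drawn once per study and requests counted up to the 845th potential recruit, the mean width was 2.41 points and the probability of a width below 3.0 was 0.89. The median N was 5,556, about 33 per centre-week. The two stated figures therefore follow from their own inputs.

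**2. What must be recorded.** Turning the formula round, a width of 2.4 points needs N = 4 × 1.96² × 0.2139 / 0.024² ≈ 5,706 requests, and 3.0 points needs about 3,652. These are all requests assessed, whether or not they met NG12. Registrations together with the 10.2 log bear on the numerator. They give no count of requests assessed that failed NG12.

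**3. Precision under 12.10.** Assumptions not fixed by the protocol: requests spread evenly over a 5-day week (250/5 = 50 to 579/5 ≈ 116 per sampled day), two months taken as 8 to 9 weeks, p = 0.31, no clustering. N = sites × weeks × requests per day.

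| Sites and duration | Requests N | 95% CI width (points) |
|---|---|---|
| One site, two months | 400–1,042 | 9.1–5.6 |
| Five sites, two months | 2,000–5,211 | 4.1–2.5 |
| One site, 52 weeks | 2,600–6,022 | 3.6–2.3 |
| One day in each of 169 centre-weeks | 8,450–19,570 | 2.0–1.3 |

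For example, one site with 50 requests a day for 8 weeks gives 3.92 × √(0.2139/400) ≈ 9.1 points. If requests are spread over 7 days, one site over two months gives 10.7–6.6 points and five sites 4.8–3.0.

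**4. A benchmark.** The existing 31% comes from 750 requests at one trust (6.5). Its width is 3.92 × √(0.2139/750) ≈ 6.6 points. One site over two months could thus be no more precise than what is already in hand.

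**The case against.** The strongest reply is that there are two separate data streams. Section 15.2 describes a count made while screening for recruitment, whereas 12.10 describes a capacity exercise that feeds 15.3, and nothing says that 12.10 is the source of the 15.2 estimate. That is a fair reading, but it does not rescue the figure: the screening stream has no recorded count of requests that failed NG12.

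A second reply is that the two-month minimum may not govern the NG12 item. It closes a paragraph about staffing and capacity, and the NG12 item sits in a later list with its own introduction and no duration. This stands. Even if the minimum applies, it is a lower limit, and the wording allows more than one site. A reader might infer that the true width will be 6–9 points, but that is only the low end of what 12.10 permits. Some readings of 12.10 do better than 2.4.

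Third, 15.2 says the study was not designed for a pre-specified precision, and in 14.1.3 this proportion carries no asterisk, so it is not among the outcomes marked as informing the definitive trial. Both points limit the consequence. They do not explain why a specific width and a 90% assurance are stated for a sample that is not collected.

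**Conclusion.** The point holds as an internal inconsistency. The stated width of 2.4 points is correct for its own scheme, but that scheme needs about 5,450 assessed requests across 169 centre-weeks, and the protocol does not record them. Under the scheme it does describe, the width runs from about 1.3 to 9.1 points depending on the number of sites and weeks, neither of which is fixed. That range assumes a 5-day week, 250–579 requests per week, p = 0.31 and no between-centre variation, which would widen every figure.

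Three stronger inferences are not supported.

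- **That the simulation assumes every request in 169 centre-weeks is assessed.** It stops at the fifth potential recruit. Assessing all 42,250–97,851 requests would give 0.88–0.58 points.
- **That 2.4 is miscalculated.** It reproduces.
- **That the value-of-information population in 16.4 depends on this estimate.** That section defines the population by NG12 referral but does not say its size will come from MEDLEY's proportion.

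**What to change.** Reconcile 10.2, 12.10, 14.1.3 and 15.2, and state which source supplies the NG12 proportion. Either of two changes would do.

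1. **Make the simulated sample exist.** Add two anonymised counts per recruiting centre-week to the monthly log return: GP chest X-ray requests assessed, and the number of those fulfilling NG12. The 15.2 figures can then stay. The cost is a small extra data-entry task at each centre. It should start with recruitment, since counts not logged at screening may be hard to recover later.
2. **Describe the sample that is collected.** Fix the number of sites and weeks for the NG12 item in 12.10, say whether the two-month minimum applies to it, and restate the width in 15.2 for one day per week. This costs wording only, but the restated width may be less favourable than 2.4 points.

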15.3 Site-level imaging data

Using these data, we will estimate the number of CT slots required to meet a range of demand percentiles, both before and after including the patients redirected from the CXR pathway. This will include the 85th percentile (which is typically used to describe the capacity required for an urgent service with variable demand). This will take into account capacity necessary to set aside ('carve-out') for emergency and surveillance procedures. We will, therefore, be able to ascertain the number of additional weekly slots required to meet the demand from the redirected patients, at any given demand percentile.

We will estimate the maximal capacity of the sites currently with respect to CT, how many additional CT tests would be required if all GP CXR requests that fulfil NG12 criteria were converted to LDCT, and alternatively the number of additional scans if conversion to LDCT was restricted to those who met a proposed 3% risk threshold.

16.0 WP2 Economic Evaluation and Value of Information Analysis Plan

A health economic analysis plan (HEAP) will be developed and reviewed by the Study Oversight Committee (SOC).

The objective of the health economic analysis is to determine whether replacing CXR with LDCT for some or all primary care referrals for suspected lung cancer is a cost-effective use of limited NHS resources. The economic evaluation will generally follow the NICE reference case for economic evaluations, in particular:

- Health effects will be captured by the quality-adjusted life year (QALY), with a preference for this to be measured among patients using the EQ-5D-5L and valued by a representative general population sample of the UK population via the time trade-off method.
- Costs will be included from the perspective of the NHS and publicly funded personal social services.
- A cost-effectiveness threshold of £20,000 to £30,000 per QALY will be used.
- A lifetime time horizon will be used.
- Future costs and QALYs will be discounted by 3.5% per year.

16.1. Collection and analysis of economic data

16.1.1 Health-related quality of life

We will collect EQ-5D-5L at baseline and 4 months. Standard descriptive and graphical analyses will be conducted as per the EuroQol manual [42]. We will calculate utility values using the most appropriate value set, which could come from the second UK EQ-5D-5L valuation study or crosswalk to the EQ-5D-3L. If both of these are available for use then the base case analysis will be dictated by the NICE position statement. We will examine differences between measures at baseline and 4 months, stratified by lung cancer status, e.g., comparing EQ-5D-5L utility at the two timepoints using the paired t-test.

16.1.2 Resource use

For each participant, we will assemble relevant data on their use of healthcare resources, including the initial imaging reports, subsequent investigations for lung cancer, subsequent investigations for incidental findings, and subsequent imaging of pulmonary nodules of indeterminate risk.

As all participants will have received CXR and LDCT, but each of these investigations will be reported independently, we will develop and apply rules to determine which healthcare resources would be used if only one of the imaging technologies had been used. For example, if the reports are LDCT1 (likely cancer – follow up in clinic) and CXR1 (likely cancer – urgent CT scan), then in the LDCT-only counterfactual there would be the cost of LDCT plus subsequent cancer investigations, while in the CXR-only counterfactual there would be the cost of CXR plus a (standard-dose) CT scan plus subsequent cancer investigations.

We will statistically summarise:

- actual resource use for participants in MEDLEY
- counterfactual resource use if only CXR used
- counterfactual resource use if only LDCT used.

16.1.3 Unit costs

Unit costs will generally be sourced from recognised sources, e.g., NHS National Cost Collection and the PSSRU Unit Costs of Health and Social Care.

As cost-effectiveness results are expected to be very sensitive to the unit costs for CXR and LDCT, we will also undertake pragmatic literature reviews and microcosting exercises to accurately estimate the unit costs for these imaging techniques.

16.2 Adaptation of lung cancer screening model

An existing Microsoft Excel economic model for cost–utility analyses of lung cancer screening will be adapted to create an economic model for the lung cancer diagnostic setting.

The model will be translated into R, with the following expected benefits:

- Improved ability to test and validate the model
- Greater flexibility (e.g., the Excel model limits the number of individuals that can be simulated in a single run)
- Improved speed of execution
- Ability to parallelise execution on a high-performance computing cluster

The structure of the model will need to be updated for use in the diagnostic setting:

- No need for subsequent imaging (except as indicated by, e.g., indeterminate nodules)
- Patients will be symptomatic and will have been referred for suspected lung cancer, which affects the pre-test probability of lung cancer (and the stage distribution of lung cancers presenting) and health-related quality of life
- Detail around the testing process will be enhanced

Various data collected from MEDLEY will be combined with data identified through pragmatic literature review and incorporated into the model:

• Distributions of patient characteristics in the diagnostic setting (age, sex, smoking status, PLCO_{m2012} lung cancer risk prediction)

- Health-related quality of life (EQ-5D-5L utility)
- Prevalence and stage distribution of lung cancer in the diagnostic population
- Subsequent investigations

16.3 Cost-utility analysis

Following adaptation of the model, a cost-utility analysis will be conducted.

Population: Patients referred from primary care with suspected lung cancer (NG12) excluding those with haemoptysis (for whom CT is already the primary investigation).

Competing options:

- CXR all: All patients receive CXR as the primary investigation
- LDCT stratified: A simple decision rule will classify patients according to their pre-test probability of lung cancer, with higher risk patients receiving LDCT as the primary investigation and lower risk patients receiving CXR as the primary investigation
- LDCT all: All patients receive LDCT as the primary investigation

Analysis details (in line with NICE reference case):

- Perspective: NHS and publicly funded personal social services
- Time horizon: Lifetime
- Discount rate: 3.5% for costs and QALYs
- Cost-effectiveness threshold: £20,000 per QALY

Parameters in the model will be subject to uncertainty and probabilistic analyses will be undertaken. Cost-effectiveness acceptability curves and distributional plots for incremental net benefit will be produced.

A budget impact analysis will not be conducted, but the results will be shown based on the expected annual population affected and the costs will be disaggregated so that the contribution of the primary investigation on costs can be seen.

16.4 Value of information analyses

We will conduct value of information analyses following the cost-utility analysis. These analyses estimate the value that can be obtained through obtaining more information about parameters of the economic model which then lead to being able to make a better policy decision. All value of information analyses will be calculated based on the incident population (the number of people referred from primary care for investigation for possible lung cancer meeting NG12 criteria) for 10 years, a willingness-to-pay of £20,000 per QALY, and discounting at 3.5% per year.

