6.2. How is lung cancer diagnosed in usual care?

Patients who have symptoms that may suggest lung cancer typically access care from general practice. NICE guidance (NG12) outlines the investigations that patients with such symptoms should receive from primary care. For all symptoms, aside from haemoptysis which accounts for less than 5% of presentations, NICE recommends patients should be investigated with chest x-ray (CXR) and those with suspicious findings referred onwards for further investigation such as computed tomography (CT)[6]. The guidance does not include recommendations on actions to take if CXR is negative; the test is therefore relied upon to triage possible lung cancer cases. CXR is cheap, quick and convenient for patients. The main downside of CXR is that it misses about 20% of lung cancers[7], causing delays to diagnosis [8].

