9.2. Exclusion Criteria for WP1

Patients will be excluded from this study for ANY of the following reasons:

- 1. Present with haemoptysis and/or have a pending urgent suspected cancer referral.
- 2. Have had thoracic CT or LDCT within the last year
- 3. Unable to, or chooses not to, receive a LDCT
- 4. Currently undergoing anti-cancer treatment.
- 5. Is pregnant* or currently breastfeeding.
- 6. Previously registered in the MEDLEY study

*Assessment of pregnancy potential (or exemption) completed as per national guidelines and/or local Trust policy.

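### Section 16.4 scales value of information by all NG12 referrals, while the model in 16.3 excludes haemoptysis: a small mismatch, at most about 5.3%, to be reconciled

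*Protocol*

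**What the plan says.** Section 16.3 sets the population for the cost-utility analysis: "Patients referred from primary care with suspected lung cancer (NG12) excluding those with haemoptysis (for whom CT is already the primary investigation"). The three options compared there (CXR for all, LDCT for higher-risk patients only, LDCT for all) differ only in whether CXR or LDCT comes first.

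Section 16.4 follows on from that analysis and fixes the multiplier for all VoI results. It is "the incident population (the number of people referred from primary care for investigation for possible lung cancer meeting NG12 criteria) for 10 years", with a willingness-to-pay of £20,000 per QALY and "discounting at 3.5% per year". Haemoptysis is not excluded, and the count is not limited to people referred for CXR. No number is given.

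Section 6.2 describes the NG12 route to CXR as applying "For all symptoms, aside from haemoptysis which accounts for less than 5% of presentations". Haemoptysis is therefore an NG12 symptom with a different first investigation.

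Section 14.2 stars the VoI assessment. Under section 14.0 a star means that the outcome informs whether to proceed to a definitive trial, or its design.

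**The concern.** The per-person value of information comes from the 16.3 model and has meaning only for people to whom the choice between CXR and LDCT applies. By 16.3's own reasoning it does not apply to haemoptysis patients. If 16.4 is followed as written, they are counted in the multiplier at full value although theirs is zero.

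Population EVPI, EVPPI and EVSI are proportional to the number of people counted, so the overcount passes straight through. Section 8.2 sets EVSI against the cost of the research to obtain the expected net benefit of sampling, and aim (b) in section 7.1 asks whether a trial's cost is justified by the information it yields. The overcount raises EVSI and leaves research cost unchanged. It therefore runs in one direction, towards the trial.

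**Working it through.** **Inputs**

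- GP-requested CXRs, England, 2021/22: 1,818,905 (section 6.5).
- Share fulfilling NG12 for urgent CXR: 31% (section 6.5).
- Stated annual number of extra CT scans: 564,000 (section 6.5). This is the only figure in the protocol that could serve as the annual incident population.
- Haemoptysis share h: below 5% of presentations (section 6.2). I assume that the share among NG12 referrals is the same.
- Horizon 10 years, discount rate 3.5% (section 16.4).

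**Step 1: reproduce the stated count.** 1,818,905 × 0.31 = 563,861, which rounds to the stated 564,000.

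**Step 2: the scaling.** Population VoI = v × N × D, where v is per-person value, N the annual number of people and D the sum of the yearly discount factors.

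- Years 0 to 9: D = Σ 1.035^(−t) = 8.608.
- Years 1 to 10: D = 8.317.

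Since v and D are the same whichever population is counted, the relative error depends on N alone.

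**Step 3: relative overstatement.** If N covers all NG12 referrals, the 16.3 population is N(1 − h), and the overstatement is 1/(1 − h) − 1.

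| h | Overstatement |
|---|---|
| 0% | 0% |
| 1% | 1.0% |
| 2% | 2.0% |
| 5% (bound from section 6.2) | 5.3% |

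**Step 4: what this means for the 564,000.** The protocol does not say whether haemoptysis was removed from the 31%, so there are two limiting cases, both shown at h = 5%.

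- *Haemoptysis is in the count.* The 16.3 population is 563,861 × 0.95 = 535,668 a year. The discounted 10-year population falls from 4.85 to 4.61 million (years 0 to 9), or from 4.69 to 4.45 million (years 1 to 10).
- *Haemoptysis is already absent, because the count is of CXR requests.* Then 563,861 is the 16.3 population and using it gives no overstatement. A count of all NG12 referrals would be at most 563,861 / 0.95 = 593,537. Taking 5% off 563,861 would remove the same patients twice and understate the value by 5%.

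**Step 5: when would it matter?** Let S be the EVSI obtained with the literal 16.4 population and C the research cost. The correct value at h = 5% is 0.95 S. The sign of the net benefit changes only if 0.95 S < C < S, that is, only if the stated EVSI exceeds the cost by less than 5.3%.

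**The case against.** The best defence is that 16.4 is loose shorthand. It comes directly after the model population has been defined, it concerns the parameters of that model, and elsewhere the protocol uses NG12 to mean CXR requests that meet NG12 (sections 9.1, 12.10, 15.2 and 15.3). An analyst who starts from the figures in section 6.5 would count CXR requests, and by section 6.2 haemoptysis is not routed to CXR. The HEAP, reviewed by the Study Oversight Committee, may settle the matter.

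Much of this stands, and it is why the lower end of the range is zero. It does not remove the point. Sections 16.4.2 and 16.4.3 leave parameter partitions and target designs to the HEAP, but the VoI population, horizon, threshold and discount rate are fixed in 16.4 itself. Nor is a count of CXR requests certain to be free of haemoptysis. WP1 recruits from GP CXR requests that fulfil NG12, yet section 9.2 still needs the exclusion "Present with haemoptysis and/or have a pending urgent suspected cancer referral", which suggests that some such requests are expected.

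A reader might go further and infer that 16.4 is also wrong because it is wider than the population MEDLEY enrols. Section 9.2 excludes, for example, people who "Have had thoracic CT or LDCT within the last year", and those on anti-cancer treatment. The documents do not support that as an error. VoI is properly scaled to the people the policy decision affects, not to those eligible for a study, and 16.3 and 16.4 agree in not applying these other exclusions. Whether MEDLEY's estimates carry over to such patients is a question of generalisability, and section 16.2 plans to combine MEDLEY data with literature. The protocol gives no share for these groups, so no size can be stated. The non-registration log (section 10.2) could not supply one reliably, because it covers only patients judged potentially eligible from the X-ray request.

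**Conclusion.** The mismatch between 16.3 and 16.4 is real but minor. Followed literally, 16.4 overstates population EVPI, EVPPI and EVSI by up to about 5.3%. If the count used is of NG12-qualifying CXR requests that already omit haemoptysis, the overstatement is about 0%.

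The upper figure rests on the bound in section 6.2, on that share applying to NG12 referrals, and on haemoptysis patients having zero value under the compared options, as 16.3 implies. It would be tempting to say that the case for a definitive trial is inflated. The protocol does not establish that: 16.4 gives no count, and a multiplier of this size alters the conclusion only when net benefit is near zero. What can be said is that the wording permits a small error in a decision-informing output, always in the trial's favour.

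**What to change.** In section 16.4 and in the HEAP, define the incident population as the 16.3 population, that is, NG12 referrals excluding haemoptysis. State the annual count that will be used and confirm that it is on that basis. If the 564,000 is used, record whether the 31% in section 6.5 was taken before or after removing haemoptysis, and adjust only if it was before.

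The cost is one phrase in each document and one check on the source of the count. No new data are needed. The downside is that the stated value of a definitive trial may become slightly less favourable.
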